### 2.1 Study Rationale

This study is being conducted to evaluate the safety, dose, pharmacokinetics (PK), pharmacodynamics (PD) and immunogenicity of intravenous (IV) SYNT001 as well as its effects on pemphigus disease activity markers.

## 2.2 Selection of Doses in this Study

The SYNT001 dose levels for study SYNT001-103 were selected following careful review of the safety, tolerability, and PD effect on total IgG levels studied in non-human primates (NHP) and healthy male subjects.

Four repeat-dose toxicology studies in cynomolgus monkeys examined 2 to 14 repeat weekly IV doses 5 to 100 mg/kg SYNT001 with up to a 4-week follow-up. There was one death in the 14-week study attributed to an immune-evoked infusion reaction, which correlated with the development of ADAs, circulating immune complexes, circulating complement depletion, and deposition of immune complexes containing SYTN001 and complement in tissues. Across studies, clinical signs were limited to reports of transient emesis/vomitus following dosing and facial flushing and periocular swelling observed in the 5-week study after the third dose coincident with the first appearance of ADAs. With the exception of emesis/vomitus, these clinical signs were effectively controlled with diphenhydramine pretreatment in the 5-week study and the subsequent 14-week study. There were no adverse SYNT001-related changes in weight gain, clinical chemistry, gross or histo-pathology. The No Observed Adverse Effect Level (NOAEL) was the highest dose tested in all 4 studies and the overall NOAEL following repeat weekly exposure to SYNT001 of up to 14 doses in cynomolgus monkeys was 100 mg/kg.

The safety, tolerability, and PD effect on total IgG levels in study SYNT-101—a Phase 1a study that assessed single ascending doses of SYNT001 in healthy male subjects—were also reviewed. In study SYNT-101, the doses of SYNT001 up to and including 30 mg/kg were well tolerated. There were no dose-limiting toxicities, serious adverse events (SAEs), or any other safety concerns. No adverse events (AEs) were observed in the 1 and 3 mg/kg dose cohorts. Headache was the most commonly reported treatment-emergent adverse event (TEAE), occurring in 8 of 11 subjects treated with 10 or 30 mg/kg SYNT001. One headache in the 10 mg/kg cohort was moderate (Grade 2) in severity; all other headaches were mild (Grade 1). One mild headache was treated with a single dose of acetaminophen; all other headaches resolved without treatment. Therefore, it is anticipated that the doses selected for this study should be well tolerated and have clinically relevant PD effects in patients with pemphigus.

Further consideration was given to the desired level of FcRn blockade to achieve suppression of IgG to a range that has been previously correlated with disease remission induced by immunoadsorption in autoimmune disorders such as pemphigus vulgaris and myasthenia gravis (ie, >50% decrease in total IgG from baseline) ([Blaha et al., 2011](#); [Eming and Hertl, 2006](#); [Kohler et al., 2011](#)).

The Sponsor also considered the potential effects of inhibiting FcRn function as they relate to IC associated innate and adaptive immunity. From the NHP studies, single doses of SYNT001 produced a dose-dependent decrease in total IgG and a further decrease was seen with repeated weekly doses up to a maximum 70% reduction at 100 mg/kg. This magnitude of total IgG reduction is approaching the expected maximal effect of 100% inhibition of FcRn function based on murine studies performed by the Sponsor and others ([Nixon et al., 2015](#); [Roopenian et al., 2003](#)). In the recently completed Phase 1a trial with SYNT001 in healthy volunteers a single dose caused a maximum average 50% drop in total IgG with IV dosing at 30 mg/kg. Based on the NHP studies further reductions are expected following multiple dosing. A comparable

decrease in pathogenic autoantibodies is anticipated. In study SYNT-101, a single dose caused a maximum average 50% drop in total IgG with IV dosing at 30 mg/kg. Based on the NHP studies, further reductions may occur following multiple dosing.

For more information on the findings from the clinical and nonclinical findings with SYNT001, please refer to the Investigator's Brochure (IB).

### **2.3 Compliance Statement**

This study will be conducted in compliance with Good Clinical Practice (GCP), including the International Conference on Harmonisation (ICH) Guidelines and FDA regulations, consistent with the principles outlined in the Declaration of Helsinki. In addition, the Investigator agrees to adhere to all applicable local laws and regulatory requirements relevant to the use of new therapeutic agents.

The study will be conducted in compliance with the protocol. The appropriate Institutional Review Boards (IRBs) must approve the protocol, any amendments, and the subject informed consent form (ICF) prior to implementation.

Freely given written informed consent must be obtained from every subject prior to participation in this clinical trial. As part of this procedure, the Investigator must explain orally and in writing the nature, duration, and purpose of the study, and the action of the drug in such a manner that the study subject is aware of the potential risks, inconveniences, or AEs that may occur. The study subject should be informed that he/she is free to withdraw from the study at any time. He/she will receive all information that is required by federal regulations and ICH guidelines. The Investigator or designee will provide the Sponsor with a copy of the IRB-approved informed consent form prior to the start of the study. The rights, safety, and well-being of participating subjects are the most important considerations and should prevail over interests of science and society.

Study personnel involved in conducting this trial will be qualified by education, training, and experience to perform their respective task(s). This trial will not use the services of study personnel where sanctions have been invoked or where there has been scientific misconduct or fraud (eg, loss of medical licensure, debarment).

### **3. STUDY OBJECTIVES AND ENDPOINTS**

#### **3.1 Primary Objective**

The primary objectives of this study are as follows:

- Safety: To evaluate the safety of once-weekly IV infusions of SYNT001 at different dose levels and dosing durations in subjects with pemphigus (vulgaris or foliaceus)
- Dose Selection: To determine a Minimum Effective Dose (MED) of SYNT001 as assessed by (i) total IgG level nadir and (ii) the proportion of subjects that meet the criteria for response by Pemphigus Disease Area Index total activity score (PDAI)

#### **3.2 Secondary Objectives**

The secondary objectives of this study are as follows:

- To determine the pharmacokinetics (PK) of SYNT001 following once-weekly IV infusions at different dose levels and dosing durations
- To evaluate the effect of once-weekly doses of SYNT001 at different dose levels and dosing durations on PD biomarkers
- To assess the effect of once-weekly doses of SYNT001 at different dose levels and dosing durations on disease markers
- To measure the immunogenicity of once-weekly doses of SYNT001 at different dose levels and dosing durations

#### **3.3 Exploratory Objectives**

The exploratory objectives of this study are as follow:

- To explore the effect of once-weekly doses of SYNT001 at different dose levels and dosing durations on biomarkers to understand the pathophysiology of the disease and the SYNT001 mechanisms of action
- To determine the impact of different SYNT001 dose levels and dosing durations on the subject's use of corticosteroids to treat their pemphigus (vulgaris or foliaceus)
- To assess the impact of once-weekly doses of SYNT001 on the subject's health-related quality of life (HR-QoL) at different dose levels and dosing durations
- To assess the effect of once-weekly doses of SYNT001 on the appearance of skin and mucosal lesions at different dose levels and dosing durations
- To quantify the amount of SYNT001 in skin (skin biopsies optional)

#### **3.4 Primary Endpoints**

The primary endpoints of this study are as follows:

Safety: The evaluation of SYNT001 safety based on vital signs, physical examinations, electrocardiograms (ECGs), clinical safety laboratory tests, the incidence of adverse events

(AEs), treatment-emergent adverse events (TEAEs) and serious adverse events (SAEs) summarized by cohort, severity, and relationship to study product

Dose Selection: The determination of dose and dosing duration of SYNT001 that achieves (i) total IgG level nadir decrease by  $\geq 60\%$  and  $\leq 90\%$  from baseline and (ii) a PDAI total activity score of  $\geq 50\%$  reduction from baseline to allow further clinical development in subject with pemphigus (*vulgaris* or *foliaceus*)

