  - k. Prior to **study drug infusion**, SYNT001 drug product is to be diluted in dextrose 5% in water (D5W) to a total volume of 250 mL and administered intravenously over 1 hour ± 15 minutes using a 0.2-micron inline filter. See [Section 4](#) and [Section 7.8](#) for additional information.
  - l. **Immunoglobulins (IgG, IgA, IgM) and IgG subtypes (IgG1-4):** Collected for measurements of IgG, IgG subtypes (IgG1-4), IgA, IgM at every visit. On Days 0, 7, 14, 21, and 28, samples are collected prior to infusion of study drug. See [Section 7.5.5](#) for additional information.
  - m. **Exploratory pharmacodynamic samples (C3 and AECA):** Collected pre-dose when collected on dosing days. See [Section 7.5.5](#) for complete information.
  - n. Buccal samples to be collected and stored; pending review of clinical and pharmacodynamics assessments.
  - o. Immunophenotyping by flow cytometry for measurement of CD3+CD4+ T, CD3+CD8+ T, monocytes, NK cells and B cells.
  - p. Photographs of active lesions taken prior to first dose on Day 0. Follow-up photographs will be taken at Days 35, 56, and 112. Subjects who begin a steroid taper will have additional photographs taken at the clinic visit during which the decision to begin the taper is made.
  - q. Subjects will return to the clinic on Days 84 and 112 for follow-up visits. Subjects whose total IgG is not within 30% of their Day 0 baseline value and not above 500 mg/dL at the Day 112 visit will be referred for further management.

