**Table 8. Pharmacodynamic Assessments**

Parameter	Collection Time Points		
	Cohort 1	Cohort 2	Cohort 3

 
IgG
 
IgG subtypes (IgG1-4)
 
IgA
 
IgM
 
	Screening and Days 0, 1, 2, 5, 7, 12, 14, 19, 21, 28, 29, 30, 33, 42, 56, 84, and 112	Screening and Days 0, 7, 14, 21, 28, 35, 42, 56, 84, and 112	Screening and Days 0, 7, 14, 21, 28, 35, 42, 49, 56, 63, 70, 77, 84, 91, 98, 105, 119, 147, and 175

 
Circulating immune complexes (CIC)
 
	Days 0, 5, 7, 12, 14, 19, 21, 28, 33, 42, 56, 84, and 112	Days 0, 7, 14, 21, 28, 35, 42, 56, 84, and 112	Days 0, 7, 14, 21, 28, 35, 42, 49, 56, 63, 70, 77, 84, 91, 98, 105, 119, 147, and 175

 
Albumin
 
	Screening and Days 0, 7, 14, 21, 28, 33, 42, 56, 84, and 112	Screening and Days 0, 7, 14, 21, 28, 35, 42, 56, 84, and 112	Screening and Days 0, 7, 14, 21, 28, 35, 42, 49, 56, 63, 70, 77, 84, 91, 98, 105, 119, 147, and 175

 
Anti-Dsg (1 and 3) antibody titers
 
	Screening and Days 0, 7, 14, 33, 56, 84, and 112	Screening and Days 0, 7, 14, 21, 28, 35, 42, 56, 84, and 112	Screening and Days 0, 7, 14, 21, 28, 35, 42, 49, 56, 63, 70, 77, 84, 91, 98, 105, 119, 147, and 175

 
C3 and AECA levels by indirect immunofluorescence
 
	Days 0, 14, 33, 56, 84, and 112	Days 0, 35, and 56	Days 0, 98, and 119

 
Exploratory biomarkers (RNAseq, urine IgG)
 
	Days 0, 14, 33, 56, 84, and 112	Days 0, 35, and 56	Days 0, 98, and 119

 
Immunophenotyping by flow cytometry for measurement of T cells, monocytes, NK cells, and B cells
 
	Days 0, 28, and 56	Days 0, 35, and 56	Days 0, 98, and 119

 
Exploratory biomarker (FCGR2A SNP, via buccal swab)
 
	Day 0	Day 0	Day 0

 
Exploratory pemphigus immune response biomarkers
 
	Days 0, 5, 7, 12, 14, 19, 21, 28, 33, 42, 56, 84, and 112	Days 0, 7, 14, 21, 28, 35, 42, 56, 84, and 112	Days 0, 7, 14, 21, 28, 35, 42, 49, 56, 63, 70, 77, 84, 91, 98, 105, 119, 147, and 175

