### Permitted Medications

Concomitant medication and treatment for co-existing conditions, including those for pemphigus, are permitted if not listed as prohibited.

1. Topical antibiotics to treat active infections that occur during the study.
2. Topical or systemic treatments for oral candidiasis.
3. Topical lidocaine for transient pain relief as needed.
4. Concomitant treatment that is medically indicated for any AEs the subject experiences during the study.
5. Medication for potential infusion reactions: The Investigator may recommend prophylactic use of acetaminophen, IV hydration, diphenhydramine, histamine2 (H2) blockers (eg, ranitidine, famotidine), etc to manage potential infusion reactions.
6. Low-strength corticosteroids (eg, hydrocortisone ≤1%) applied to a single lesion contributing <10% of the PDAI total activity score.
7. Topical tacrolimus, sirolimus or pimecrolimus applied to a single lesion contributing <10% of the PDAI total activity score.

8. Dexamethasone elixir solution for oral lesions if dose remains stable throughout trial participation (swish and spit only).
9. Stable regimen of the following systemic immunosuppressants: azathioprine, mycophenolate mofetil, methotrexate, dapsone, cyclosporine, tacrolimus, sirolimus, or low dose oral cyclophosphamide ( $\leq 100$  mg/day).

One month after the final dose of SYNT001, corticosteroids may be tapered at the Investigator's discretion.

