### 10.3.3 Potential Immune Effects

An antibody blocking FcRn is anticipated to have several effects. These include acceleration of catabolism of IgG, but not other immunoglobulin isotypes such as IgA and IgM, leading to dose-dependent decreases in circulating IgG levels by up to an estimated 50% from the baseline levels after a single dose and further decreases after multiple doses up to a 70% to 80% reduction. Based on studies in humans, it is expected that with a single dose, the nadir of this effect will

occur approximately 5 days after dosing. The time course of recovery of IgG following dosing in the Phase 1a study suggests that a return to within 30% of baseline levels observed at pretreatment occurs within 4 weeks after a single dose and within 4 weeks after multiple doses as shown in NHPs.

Given the normal adult range of total IgG of 500 to 1600 mg/dL (Agarwal and Cunningham-Rundles, 2007; Furst, 2009; Gonzalez-Quintela et al., 2008; Jolliff et al., 1982; Keystone et al., 2007; McMillan et al., 1997; van Vollenhoven et al., 2013), with a mean of 1150 mg/dL, a 50% decrease in the mean would be to 575 mg/dL and a 50% decrease from the low end of the normal range used for the inclusion criteria of 600 mg/dL in this study would be to 300 mg/dL. An 80% decrease from baseline after multiple doses would result in IgG levels of 230 mg/dL and 120 mg/dL, respectively. While these levels are in the range found in patients with primary humoral immunodeficiency (Ameratunga et al., 2013), the levels will be transient. Further, as reported for other therapies used for pemphigus, the temporary (ie, less than 4 months) depletion of IgG (up to 95% reduction of total IgG as seen with immunoadsorption) does not appear to impart an increased risk of infection (Eming and Hertl, 2006; Furst, 2009; Keystone et al., 2007; Schmaldienst et al., 2001; van Vollenhoven et al., 2013). Study subjects will be monitored clinically for any infection. Further, commercial IVIG can be given to reverse the low IgG levels in case of a bacterial infection occurring while their IgG levels are decreased.

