#### **11.4.3.2 Dose Selection Data**

The evaluation of SYNT001 based on total IgG levels and responses on the PDAI total activity score from baseline will be summarized using descriptive statistics. Descriptive statistics will include mean, SD, coefficient of variation (CV), median, minimum, and maximum. The determination of dose and dosing duration of SYNT001 that achieves (i) total IgG level nadir decrease by  $\geq 60\%$  and  $\leq 90\%$  from baseline and (ii) a PDAI total activity score of  $\geq 50\%$  reduction from baseline to allow further clinical development in subject with pemphigus (*vulgaris* or *foliaceus*).

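### The IgG nadir criterion is a minimum over sampling schedules that differ by cohort, so an identical effect reads a few points deeper in the 10 mg/kg cohort than in Cohort 2

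*Protocol*

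**What the plan says.** Section 3.4 defines the dose-selection endpoint as "The determination of dose and dosing duration of SYNT001 that achieves (i) total IgG level nadir decrease by" 60 to 90%, together with a PDAI total activity score showing at least a 50% "reduction from baseline to allow further clinical development in subject with pemphigus". Section 11.4.3.2 repeats both criteria and says that "responses on the PDAI total activity score from baseline will be summarized using descriptive statistics". Neither place names a visit, a window or a set of visits common to the cohorts.

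Table 8 gives the IgG schedules:
- Cohort 1: "Screening and Days 0, 1, 2, 5, 7, 12, 14, 19, 21, 28, 29, 30, 33, 42, 56, 84, and 112"
- Cohort 2: "Screening and Days 0, 7, 14, 21, 28, 35, 42, 56, 84, and 112"
- Cohort 3: screening, Day 0, weekly from Day 7 to Day 105, then Days 119, 147 and 175.

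The footnote to Table 3 adds, for Cohort 2: "On Days 0, 7, 14, 21, and 28, samples are collected prior to infusion of study drug". Table 4 has the same rule for Cohort 3. Section 10.3.3 states that "it is expected that with a single dose, the nadir of this effect will" come about 5 days after dosing.

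On PDAI, Tables 2 to 4 schedule 9, 9 and 18 post-baseline assessments. Section 7.12 says: "One month after the final dose of SYNT001, corticosteroids may be tapered" at the investigator's discretion.

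**The concern.** The objective in section 3.1 is a minimum effective dose, reached by holding cohorts with different doses and durations against one IgG window. The measuring instrument differs between them. Cohort 1 is read close to the expected low point of each dosing interval, while Cohorts 2 and 3 are read after recovery has begun. Cohort 1 is also the lowest dose, so the difference leans towards finding that dose sufficient.

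A later analysis plan can choose which visits to use, but it cannot supply 5-day samples that Cohorts 2 and 3 never schedule. Section 11.4.1 requires the SAP only before database lock, whereas the Dose Escalation Committee uses total IgG during the study. Cohorts 2 and 3 start with 4 subjects each, so if the window is applied subject by subject, one reclassified subject moves the proportion by 25 points.

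**Working it through.** The protocol gives no figure to reproduce: section 11.3 states that no formal sample size calculation was done.

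**Counts (Table 8, nominal days)**

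| | Post-baseline IgG samples | Shortest scheduled gap after a dose | Samples 5 days after a dose |
|---|---|---|---|
| Cohort 1 | 16 | 1 day (Days 1, 29) | Days 5, 12, 19, 33 |
| Cohort 2 | 9 | 7 days | none |
| Cohort 3 | 18 | 7 days | none |

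Optional Cohort 4 has no schedule table and is left out.

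**Simple turnover model.** Assumptions: IgG half-life 21 days, so k = ln 2 / 21 = 0.0330 per day. Each weekly dose multiplies IgG loss by (1 + S) for 5 days, which puts the single-dose nadir at Day 5. The effect is the same in every cohort, with no noise. With IgG as a fraction of baseline:

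- 5 days after dose j: N = f + (P − f)·a, where P is the level just before that dose (1 before the first), f = 1/(1 + S) and a = exp(−5k(1 + S))
- 7 days after dose j, before the next dose: P = 1 − (1 − N)·b, where b = exp(−2k) = 0.936

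S = 2.38 gives f = 0.296, a = 0.572 and a five-dose nadir of 62%:

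| Dose | Fall at 5 days | Fall at 7 days |
|---|---|---|
| 1 | 30.1% | 28.2% |
| 2 | 46.2% | 43.3% |
| 3 | 54.9% | 51.4% |
| 4 | 59.5% | 55.7% |
| 5 | 62.0% | 58.0% |

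Cohort 1 records 62.0% (Day 33) and meets 60%. Cohort 2 records 58.0% (Day 35) and does not. Over 14 weekly doses, the same effect reads at most 60.7% in Cohort 3.

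**Where the classification changes.** The 7-day fall is 0.936 times the 5-day fall, so Cohort 2 misses 60% whenever the true fall is below 60/0.936 = 64.1%. With a 28-day half-life the factor is 0.952 and the limit is 63.0%.

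**Sensitivity to the kinetics.** Let the drug effect c decay exponentially and act through c/(c + 0.3), with the peak after one dose set to 1. True five-dose nadir 62%:

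| Effect half-life (days) | Single-dose nadir, fitted to a 50% fall | Cohort 1 | Cohort 2 |
|---|---|---|---|
| 0.5 | Day 3.1 | 62.0% | 54.2% |
| 1.0 | Day 5.2 | 61.3% | 57.5% |
| 1.5 | Day 7.1 | 61.5% | 59.5% |
| 2.0 | Day 8.7 | 61.9% | 60.6% |

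Over true nadirs of 60 to 65% the gap runs from 1.2 to 8.2 points. With loss proportional to c instead, the four pairs are 61.8/53.2, 61.9/55.8, 61.7/57.5 and 61.5/58.6. Models with the single-dose nadir near Day 5 give a gap of about 4 points.

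**Number of draws.** With a flat true fall of 57% and 7, 4 and 13 samples near the plateau, the chance of recording at least 60% is 0.46, 0.36 and 0.57 at an assumed 5% CV, and 0.70, 0.60 and 0.79 at 10%.

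**Shared visits.** Days 7, 14, 21 and 28 are pre-dose on the same dosing schedule in all three cohorts, so an identical effect reads identically. In the simple model the deepest of these is 55.7% (Day 28), which is 6.3 points below the 62.0% nadir.

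**PDAI.** If response counted at any visit, with an illustrative 10% chance per independent visit, 9 visits give 1 − 0.9⁹ = 0.61 and 18 give 1 − 0.9¹⁸ = 0.85. Autocorrelated versions put Cohort 3 higher by 0.11 to 0.13. The last visit is 84 days after the last dose (112 − 28; 175 − 91), about 8 weeks after taper becomes permissible.

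**The case against.** A reader might infer that the same effect will pass in one cohort and fail in another whatever its size. The documents do not support that. Section 2.2 reports a 50% average fall after a single 30 mg/kg dose, and fitting the simple model to it (S = 4.66) gives 78.5% in Cohort 1 and 73.5% in Cohort 2. Section 10.3.3 anticipates falls of up to 70 to 80% on repeat dosing, and a true 70% reads 70.0% and 65.5%. Both cohorts pass in both cases. A change of classification needs a nadir just above 60%. That is plausible at a lower dose, but it is a narrow band.

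Other objections that stand in part:
- The 5-day figure is a single-dose statement, so applying it to repeat dosing is an extrapolation.
- Visit windows of ±1 day in Cohorts 2 and 3 allow an occasional 5-day gap (dose on Day 29, sample on Day 34). None is scheduled.
- Section 11.4.3.2 is descriptive, IgG is also summarised by timepoint, and the committee weighs safety and clinical outcomes too. No mechanical rule ranks the cohorts.
- For PDAI, Cohorts 1 and 2 differ only by Day 33 against Day 35, which is immaterial. Cohort 3's extra visits follow from the longer dosing under study. The protocol states neither an any-visit nor a last-visit reading, and the assessment day can properly be set in the SAP.

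What remains is that a minimum over unequal schedules is not comparable between cohorts, and both the endpoint and the schedules are set in the protocol.

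**Conclusion.** The IgG point holds. Read as written, the primary IgG criterion favours Cohort 1 over Cohort 2 by about 1 to 8 points for an identical effect, and by about 4 points under kinetics that match the protocol's own expected nadir time. It can alter the 60% classification when the true nadir is roughly 60 to 64%. That band widens if the drug effect wears off faster and narrows if it wears off more slowly. The sample counts and dose-to-sample gaps come from the protocol. The half-lives, effect shapes and CVs are assumptions. The PDAI point is secondary and concerns only Cohort 3, and only if response is read over any visit. This should be fixed, but it is not a defect that invalidates the trial.

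**What to change.** In sections 3.4 and 11.4.3.2:
- Base the between-cohort IgG comparison on percent fall at shared pre-dose visits: Days 7, 14, 21 and 28 in all cohorts. Add Day 42 for Cohort 1 against Cohort 2 only, since Cohort 3 is still being dosed then.
- For duration, compare pre-dose Day 91 with pre-dose Day 28 within Cohort 3 subjects.
- Keep the full-schedule nadir for the 60 to 90% window, and state that Cohort 1 is sampled nearer the nadir.
- Do not apply the 60% line unchanged to shared-visit values. They read about 6 points lower, so true passes would fail in every cohort.
- For PDAI, use one visit per regimen before taper is permissible (Day 33 or 35 for five doses, Day 98 for fourteen), with Day 28 for comparison across cohorts.

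The cost is wording and one extra summary, with no new samples. Cohort 1's Day 5, 12, 19 and 33 samples would no longer count in the between-cohort comparison.
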